8.1.1 Escalation stopping criteria

After all subjects have completed Visit 4 in a given cohort, the PI will evaluate if any of the following have occurred in individual subjects:

- Time in low interstitial glucose (defined as below 54 mg/dL (3.0 mmol/L)) is higher than 2% of the total time from initiation of treatment (day 1) to end of treatment (day 7) on the same t_{\max} , or,
- One or more episodes of treatment emergent severe hypoglycaemia (see [Appendix 7](#) for definition) have occurred from initiation of treatment (day 1) to end of treatment (day 7) on the same t_{\max}

For each subject and for each treatment period, the time in low interstitial glucose (percentage) and number of treatment emergent severe hypoglycaemia episodes as per the above evaluation must be recorded in the CRF.

Escalation decision

If any of the above specified events occur in two or more subjects on the same t_{\max} setting within a cohort, continuation to the next cohort with a lower t_{\max} setting will not occur. Concretely, continuation to the next cohort with a lower t_{\max} setting will not occur in the following scenarios:

- Time in low interstitial glucose (defined as below 54 mg/dL (3.0 mmol/L)) is higher than 2% of the total time from initiation of treatment (day 1) to end of treatment (day 7) on the same t_{\max} in two or more subjects,
- One or more episodes of treatment emergent severe hypoglycaemia (see [Appendix 7](#) for definition) have occurred from initiation of treatment (day 1) to end of treatment (day 7) on the same t_{\max} in each of two or more subjects,
- Time in low interstitial glucose (defined as below 54 mg/dL (3.0 mmol/L)) higher than 2% of the total time from initiation of treatment (day 1) to end of treatment (day 7) on the same t_{\max} in one or more subjects and one or more episodes of treatment emergent severe hypoglycaemia (see [Appendix 7](#) for definition) have occurred from initiation of treatment (day 1) to end of treatment (day 7) on the same t_{\max} in one or more subjects.

The escalation decision at the end of the cohort must be documented by the PI. If the escalation decision is to not open the next cohort, then the subjects who are in screening will be registered as withdrawn and an end-of-trial form must be completed.

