8.1.2 Temporary discontinuation of trial treatment

During the temporary discontinuation of trial treatment, subject should be treated as per PI's discretion and the Fiasp[®] pen included in the back-up kit may be used. In a scenario where the iLet[™] is replaced or restarted due to any technical reasons, subject will not be required to have an "in-patient" period again.

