9.1 Efficacy assessments

The endpoints and derivations calculated based on the interstitial glucose profiles will be assessed using the data collected on the iLet™, see section [9.12](#).

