10.3.1 Primary endpoint

The primary objective of the trial is to investigate the safety of selected t_{\max} settings in the insulin-only configuration of the iLet™ bionic pancreas using fast-acting insulin aspart in adults with T1DM in a short-term, outpatient clinical trial. The primary endpoint to address this objective is:

- Time in low interstitial glucose (defined as below 54 mg/dL [3 mmol/L]) from initiation of treatment (day 1) to end of treatment (day 7) (percentage)

This will be derived as the percentage of available interstitial glucose values below 54 mg/dL (3 mmol/L)

The assessment of the primary endpoint will be based on descriptive summaries presenting mean, median, minimum and maximum values by cohort and treatment.

Supplementary analysis for the primary analysis

The default t_{\max} setting (t_{65}) will be compared to each of the non-default t_{\max} settings (t_{50} , t_{40} and t_{30}) separately by cohort for time spent in low interstitial glucose (defined as below 54 mg/dL [3mmol/L]) using a linear mixed effect model with treatment and period as fixed effects and subject as random effect. This is done to investigate the treatment differences from a within-subject perspective.

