Number of self-manageable (able to self-treat) treatment-emergent hypoglycaemic episodes that require oral carbohydrate intervention per day from initiation of treatment (day 1) to end of treatment (day 7) (count)

Treatment emergent self-manageable (able to self-treat) hypoglycaemic episodes that require oral carbohydrate intervention per day will be calculated as the sum of all treatment-emergent hypoglycaemic episodes where the subject is able to self-treat and that require oral carbohydrate intervention divided by the actual duration of the treatment period in days. It will be presented using descriptive statistics made by cohort and treatment.

Number of treatment-emergent adverse events from initiation of treatment (day 1) to end of treatment (day 7) (count)

Adverse events will be coded using the Medical Dictionary for Regulatory Activities (MedDRA) and will be presented based on system organ class and preferred terms.

Treatment-emergent: adverse events will be defined as treatment-emergent, if the onset of the event occurs in the on-treatment period

Treatment-emergent adverse events will be presented in terms of the number of subjects with at least one event (N), the percentage of subjects with at least one event (%), the number of events (E) and the event rate per 100 years of exposure (R) made by cohort and treatment. These summaries are done by seriousness, severity, relation to trial product, adverse events leading to discontinuation of trial treatment and outcome.

Furthermore, summary tables based on system organ class and preferred terms are made for:

- All treatment-emergent adverse events
- Serious treatment-emergent adverse events

- Possibly and probably related treatment-emergent adverse events
- Severe treatment-emergent adverse events

All adverse events will be listed with information on when it occurred.

Number of treatment-emergent infusion site reactions from initiation of treatment (day 1) to end of treatment (day 7) (count)

Treatment-emergent infusion site reactions will be summarised by cohort and treatment.

Total insulin dose (U/kg) per day from initiation of treatment (day 1) to end of treatment (day 7) (U/Kg/day)

Total daily insulin dose will be calculated as the sum of all insulin doses delivered by the iLet™ divided by the actual duration of the treatment period in days. It will be presented using descriptive statistics made by cohort and treatment.

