10.3.4.3 Escalation decision

For each of the two escalation stopping criteria defined in section [8.1.1](#) , the number and percentage of subjects fulfilling the criteria will be presented separately by cohort and treatment.

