Subjects should be instructed to avoid medications with acetaminophen/paracetamol while wearing the CGM sensor. These medications may affect the performance and readings of the CGM sensor (e.g. false high CGM readings)⁷⁻⁹. *If a subject inadvertently takes acetaminophen during the trial, they will be instructed to contact study staff. Site staff will closely monitor their CGM readings and instruct the subject to measure BG using the BG meter to verify CGM readings as frequently as needed. If the BG is closely correlated with the subject’s CGM glucose, study staff will continue to monitor closely. If CGM glucose is consistently higher than BG by >20 mg/dL(1.1 mmol/L) for BG ≤100 mg/dL (5.55 mmol/L) or >20% for BG >100 mg/dL(5.55 mmol/L), then the study staff may temporarily discontinue the iLet™ for the duration of action of the acetaminophen.*

Also, subject should be instructed to remove the Dexcom G5 sensor, transmitter, and receiver before x-ray, Magnetic Resonance Imaging (MRI), Computed Tomography (CT) scan, or high-frequency electrical heat (diathermy).

Section 9.13: Back-up Kits

- ~~Fiasp® FlexTouch® pen injector (supplied by Novo Nordisk)~~
- ~~Needles (to be used with Fiasp® pen injector FlexTouch®)~~
- ~~Urine sticks for ketone monitoring~~

Subjects will also be encouraged to always carry the BG - meter, *Ketone meter* and test strips.

Section 9.15: Discharge criteria

The discharge of subjects from the “in-patient” period (during which subjects will be at a designated place such as a hotel) is at the discretion of the PI. In order to make the evaluation whether it is safe for the subjects to continue to the “out-patient” period of the trial, the PI may rely on data that include but are not limited to: hypoglycaemic episodes, the number of times carbohydrates are taken by subjects to prevent or treat hypoglycaemic episodes and time in low interstitial glucose (defined as < 54 mg/dL; 3 mmol/L). *Subjects will not be discharged if they have any severe hypoglycaemic episode possibly/probably related to investigational medicinal product and/or investigational medical device in the last 24 hours.*

In the event of diabetic ketoacidosis or ≥ 2 episodes of severe hypoglycaemia, possibly/probably related to investigational medicinal product and/or investigational medical device, the subject will discontinue the trial treatment as per section 8.1.

Section 9.16: Remote Monitoring

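### Section 8.1.1 words the 2% escalation limit on total time while 10.3.1 uses available readings, and 10.3.2.1 divides iLet-only insulin by the whole treatment period

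*Combined protocol and SAP*

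**What the plan says.** **Escalation criterion (protocol 8.1.1).** A subject meets the glucose criterion when time below 54 mg/dL "is higher than 2% of the total time from initiation of treatment (day 1) to end of treatment (day 7") on one t_max setting. The same denominator appears three times: once in the criterion and twice in the scenarios that block the next cohort. The PI applies the rule after all subjects in a cohort have completed visit 4. Each subject's percentage in each period, "as per the above evaluation must be recorded in the CRF". Escalation stops when two or more subjects on the same setting meet a criterion.

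**Primary endpoint (protocol 10.3.1).** For the percentage with the same name, threshold and window: "This will be derived as the percentage of available interstitial glucose values below 54 mg/dL (3 mmol/L"). Under 9.1, the glucose endpoints "will be assessed using the data collected on the iLet™". Under 10.3.4.3, for each stopping criterion, "the number and percentage of subjects fulfilling the criteria will be presented separately by cohort and treatment".

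**Insulin dose (protocol 10.3.2.1).** Total daily dose is the "sum of all insulin doses delivered by the iLet™ divided by the actual duration of the treatment period in days".

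**Time off the iLet within a period.** The plan allows three routes, none with a maximum duration in hours:
- Temporary discontinuation (8.1.2), when the Fiasp "pen included in the back-up kit may be used".
- Inadvertent acetaminophen with discrepant CGM readings (9.10 as changed by Protocol Amendment 1): "then the study staff may temporarily discontinue the iLet™ for the duration of action of the acetaminophen".
- CGM connectivity not re-established after 6 hours (9.16 as changed by Protocol Amendment 1): the subject moves to usual CSII until staff can assess device and subject in person.

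The treatment period nevertheless runs from the staff start of the iLet to the staff stop at the next visit (9.12, 10.2), with no deduction for such time.

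**The concern.** One named percentage has two stated denominators. They coincide when the glucose record is complete and separate when readings are missing. Dividing low time by total time then treats each unobserved minute as not low, so a subject can only look better under the literal 8.1.1 wording than under 10.3.1. That leans toward opening a lower t_max setting, and section 3.3 names too low a setting as a possible cause of hypoglycaemia through insulin stacking.

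Timing matters. Under 10.3 a SAP is optional and need only be final before database lock. The escalation decisions are taken earlier, cohort by cohort, so only the protocol text can settle their denominator in time.

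The dose endpoint has a related mismatch. Its numerator stops when the iLet is off and its denominator does not. No decision depends on it.

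**Working it through.** The plan gives no sample size calculation or error rate for this rule, so there is no figure of its own to reproduce. The check is arithmetic on the denominators.

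**Inputs**
- Period length T = 7 days = 168 h = 10,080 min (5.1).
- Limit 2% (8.1.1).
- One glucose value per 5-minute step. This is an assumption: 3.2.1 gives 5 minutes as the dosing step.
- h = hours with no stored glucose value, or hours off the iLet for the dose. The values 6, 12 and 24 are assumptions. Six hours is the connectivity limit in amended 9.16.

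**Escalation limit.** Under 8.1.1 read literally, percentage = low minutes / (60T). Under 10.3.1, percentage = low minutes / (60(T − h)). The literal rule therefore trips only above 2% × T/(T − h) of available readings.

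A full period holds 168 × 12 = 2,016 readings. Two percent is 40.32 readings (201.6 min), so 41 low readings are needed under total time, whatever is missing.

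| h missing | Readings available | 2% of these | Low readings needed on available values | Literal limit on available-reading scale | Counts where the wordings disagree | Band, 0.02 × h |
|---|---|---|---|---|---|---|
| 6 | 1,944 | 38.88 | 39 | 2% × 168/162 = 2.07% | 39–40 | 7.2 min |
| 12 | 1,872 | 37.44 | 38 | 2% × 168/156 = 2.15% | 38–40 | 14.4 min |
| 24 | 1,728 | 34.56 | 35 | 2% × 168/144 = 2.33% | 35–40 | 28.8 min |

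Example: 38 low readings with 24 h missing give 38/2,016 = 1.88% (not flagged) and 38/1,728 = 2.20% (flagged).

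The flowchart's visit window allows a 6-day period (T = 144 h). The literal limits are then 2% × 144/138 = 2.09%, 2% × 144/132 = 2.18% and 2% × 144/120 = 2.40%.

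If values are still stored throughout the interruption, h = 0 for this purpose and both wordings give 2.00%.

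**Dose.** At a constant delivery rate while the iLet is on, reported dose = rate × (T − h)/T, so the understatement is h/T: 6/168 = 3.6%, 12/168 = 7.1%, 24/168 = 14.3%. If one of eight subjects with similar doses is affected, the mean for that setting falls by one eighth of this: 0.4%, 0.9% or 1.8%.

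**The case against.** *Total time* may only name the observation window: the whole 7-day period rather than one day or the out-patient part. The CRF item in 8.1.1 matches the primary endpoint by name, threshold and window, 10.3.1 says how that endpoint is derived, and Table 10–1 derives the other glucose percentages from available values too. No text instructs anyone to score unobserved minutes as not low. This stands as a reasonable account of intent, but no cross-reference says so and the literal denominators differ.

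A reader might infer that every hour off the iLet is an hour of missing glucose. The documents do not support that. The CGM sensor and StudyPhone are separate devices (7.1.2), and staff keep watching CGM readings during an acetaminophen episode (amended 9.10). Whether a paused iLet still stores values is not stated. A poor network may interrupt remote monitoring without losing iLet data. The connectivity route is the clearest case for missing values. Even there, an alert after 15 minutes, and a sensor replacement requested if recovery fails within 20–30 minutes, should shorten most gaps.

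Safety also does not rest on this rule alone: there is 24-hour remote monitoring (9.16), and Amendment 1 adds individual discontinuation and trial stopping criteria.

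On the dose, the quantity is fully specified and reproducible, and dividing by time on the iLet describes something slightly different. That is fair, but the endpoint is labelled a total daily dose and omits pen and CSII insulin while keeping their hours in the denominator.

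**Conclusion.** The point holds as a minor inconsistency worth correcting. Read literally, and only when readings are missing, 8.1.1 raises the limit on the available-reading scale from 2% to about 2.07%, 2.15% or 2.33% with 6, 12 or 24 h missing. The direction always favours escalation. The two wordings classify a subject differently only within a band of about 7, 14 or 29 minutes of low glucose in a 7-day period.

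A reader might infer that an escalation decision is likely to be wrong. The documents do not support that either. Under the two-subject rule, one reclassified subject changes the decision only if exactly one other subject on that setting meets a criterion. No interruption frequency is given, so no probability can be stated.

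The dose understatement is certain in direction whenever the iLet is off, at 3.6% to 14.3% for the affected subject under a constant rate. It concerns a descriptive supportive endpoint only.

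The results rest on the assumed hours and, for the reading counts, on one reading per 5 minutes.

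**What to change.** 1. **Protocol 8.1.1, before the first escalation decision.** In all three places, replace *of the total time* with *of the available interstitial glucose values, derived as in section 10.3.1*. The cost is a wording change. The rule becomes marginally stricter for subjects with missing readings, and their percentage rests on fewer values, as it already does in 10.3.1.
2. **Protocol 10.3.2.1 or the SAP.** Divide iLet-delivered insulin by treatment duration minus time off the iLet. Do not subtract time when the iLet is running and gives no insulin. There is no dedicated field for off-iLet intervals. They would be inferred from the time-stamped iLet records, including delivery status (9.12), and from the site-contact dates, times and reasons (9.16). This takes some derivation work and judgement, because a gap in the records may also be lost data. The listed diary items and iLet parameters do not capture pen or CSII doses, so adding these to the numerator is not a practical alternative.
3. **Optional, in the SAP.** Glucose values stored while the subject is on pen or CSII still count toward the t_max setting under both rules, and change 1 does not alter that. A descriptive sensitivity summary excluding them, for both the primary endpoint and the 2% criterion, would show whether they matter.

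None of this needs a new visit, CRF page or subject.

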8.1.2 Temporary discontinuation of trial treatment

During the temporary discontinuation of trial treatment, subject should be treated as per PI's discretion and the Fiasp[®] pen included in the back-up kit may be used. In a scenario where the iLet[™] is replaced or restarted due to any technical reasons, subject will not be required to have an "in-patient" period again.

8.1.3 Rescue criteria

The criteria for the use of rescue medication should be as per investigator's discretion. Please see section [7.7.1](#) for the description of rescue medication.

8.2 Withdrawal from the trial

Final drug accountability must be performed even if the subject is not able to come to the trial site.

If a subject withdraws from the trial, he/she may request destruction of any samples taken and not tested, and the investigator must document this in the medical record.

If the subject withdraws consent, Novo Nordisk may retain and continue to use any data collected before such a withdrawal of consent.

Although a subject is not obliged to give his/her reason(s) for withdrawing, the investigator must make a reasonable effort to ascertain the reason(s), while fully respecting the subject's rights. Where the reasons are obtained, the primary reason for withdrawal must be specified in the end of trial form in the CRF.

8.2.1 Replacement of subjects

Subjects who discontinue trial treatment or withdraw from trial will not be replaced.

8.3 Lost to follow-up

A subject will be considered lost to follow-up if he or she repeatedly fails to return for scheduled visits and is unable to be contacted by the trial site.

The following actions must be taken if a subject fails to return to the trial site for a required visit:

- The site must attempt to contact the subject and reschedule the missed visit as soon as possible and counsel the subject on the importance of maintaining the assigned visit schedule and ascertain whether or not the subject wishes to and/or should continue in the trial.
- Before a subject is deemed lost to follow-up, the investigator must make every effort to regain contact with the subject (where possible, at least three telephone calls and, if

- necessary, a certified letter to the subject's last known mailing address or local equivalent methods). These contact attempts should be documented in the subject's source document.
- Should the subject continue to be unreachable, he/she will be considered to have withdrawn from the trial with a primary reason of lost to 'follow-up'.

9 Trial assessments and procedures

- Trial procedures and their timing are summarised in the flowchart, see section [2](#).
- Informed consent must be obtained before any trial related activity, see [Appendix 3](#).
- All screening evaluations must be completed and reviewed to confirm that potential subjects meet all eligibility criteria.
- The investigator will maintain a screening log to record details of all subjects screened and to confirm eligibility or record reason for screen failure, as applicable.
- At screening, subjects will be provided with a card stating that they are participating in a trial and giving contact details of relevant trial site staff.
- Adherence to the trial design requirements, including those specified in the flowchart, is essential and required for trial conduct.
- Review of completed diaries must be documented either on the documents or in the subject's source documents. If clarification of entries or discrepancies in the diary is needed, the subject must be questioned and a conclusion made in the subject's source documents. Care must be taken not to bias the subject.
- Repeat samples may be taken for technical issues and unscheduled samples or assessments may be taken for safety reasons. Please refer to [Appendix 2](#) for further details on laboratory samples.

9.1 Efficacy assessments

The endpoints and derivations calculated based on the interstitial glucose profiles will be assessed using the data collected on the iLet™, see section [9.12](#).

9.1.1 Clinical efficacy laboratory assessments

There are no laboratory assessments related to clinical efficacy.

9.2 Adverse events

The definitions of AEs and SAEs can be found in [Appendix 4](#).

The investigator is responsible for detecting, documenting, recording and following up on events that meet the definition of an AE or SAE.

9.2.1 Time period and frequency for collecting AE and SAE information

All AEs will be collected from the first trial-related activity after obtaining informed consent and until the follow up visit, at the time points specified in the flowchart.

All SAEs will be recorded and reported to Novo Nordisk or designee within 24 hours, as indicated in [Appendix 4](#). The investigator must submit any updated SAE data to Novo Nordisk within 24 hours of it being available.

[figure not shown]
Investigator is not obligated to actively seek for AE or SAE in former trial subjects. However, if the investigator learns of any SAE, including a death, at any time after a subject has been discontinued from/completed the trial, and the investigator considers the event to be possibly/probably related to the investigational trial product or trial participation, the investigator must promptly notify Novo Nordisk.

The method of recording, evaluating and assessing causality of AE and SAE and the procedures for completing and transmitting SAE reports are provided in [Appendix 4](#).

In order for Novo Nordisk to perform a complete investigation of reported SAEs, Novo Nordisk might ask the investigator to complete a technical complaint form. For reporting of technical complaints, see [Appendix 6](#).

Timelines for reporting of AEs are listed in [Figure 9-1](#).

Some AEs require additional data collection via a specific event form. This includes medication errors observed during the trial. The relevant specific events are listed in [Table 9-1](#) and the reporting timelines in [Figure 9-1](#).

Timelines are from the awareness of an AE.
Queries and follow-up requests to be resolved ≤ 14 calendar days.
AE: Adverse Events, SAE: Serious Adverse Events, SIF: Safety Information Form

Figure 9–1 Decision tree for determining the event type and the respective forms to complete with associated timelines

Table 9–1 AEs requiring additional data collection (via specific event form)

Event type	AE requiring additional event form
Hypoglycaemic episode ^a	X
Infusion site reaction ^b	X
Medication error ^c	X

^a Non-serious hypoglycaemic episode should only be reported on the hypoglycaemic episode form. Hypoglycaemic episode qualifying as a SAE should be reported on the AE form, SIF and Hypoglycaemic episode form. Refer to Section 9.2.6 and Appendix 4 for reporting details

^b Refer to Section 9.4.3 and Appendix 4 for reporting details

^c Refer to Appendix 4 for reporting details

